APPENDIX 5 MANAGEMENT ALGORITHMS FOR IMMUNO-ONCOLOGY AGENTS

These general guidelines constitute guidance to the Investigator and may be supplemented by discussions with the Medical Monitor representing the Sponsor. The guidance applies to all immuno-oncology agents and regimens.

A general principle is that differential diagnoses should be diligently evaluated according to standard medical practice. Non-inflammatory etiologies should be considered and appropriately treated.

Corticosteroids are a primary therapy for immuno-oncology drug-related adverse events. The oral equivalent of the recommended intravenous doses may be considered for ambulatory patients with low-grade toxicity. The lower bioavailability of oral corticosteroids should be taken into account when switching to the equivalent dose of oral corticosteroids.

[figure not shown]
Consultation with a medical or surgical specialist, especially prior to an invasive diagnostic or therapeutic procedure, is recommended.

The frequency and severity of the related adverse events covered by these algorithms will depend on the immuno-oncology agent or regimen being used.

Updated: 05-Jul-2016

GI Adverse Event Management Algorithm

Rule out non-inflammatory causes. If non-inflammatory cause is identified, treat accordingly and continue I-O therapy. Opiates/narcotics may mask symptoms of perforation. Infliximab should not be used in cases of perforation or sepsis.

[figure not shown]

Patients on IV steroids may be switched to an equivalent dose of oral corticosteroids (e.g. prednisone) at start of tapering or earlier, once sustained clinical improvement is observed. Lower bioavailability of oral corticosteroids should be taken into account when switching to the equivalent dose of oral corticosteroids.

Updated 05-Jul-2016

Renal Adverse Event Management Algorithm

Rule out non-inflammatory causes. If non-inflammatory cause, treat accordingly and continue I-O therapy

[figure not shown]

Patients on IV steroids may be switched to an equivalent dose of oral corticosteroids (e.g. prednisone) at start of tapering or earlier, once sustained clinical improvement is observed. Lower bioavailability of oral corticosteroids should be taken into account when switching to the equivalent dose of oral corticosteroids.

Updated 05-Jul-2016

Pulmonary Adverse Event Management Algorithm

Rule out non-inflammatory causes. If non-inflammatory cause, treat accordingly and continue I-O therapy. Evaluate with imaging and pulmonary consultation.

[figure not shown]

Patients on IV steroids may be switched to an equivalent dose of oral corticosteroids (e.g. prednisone) at start of tapering or earlier, once sustained clinical improvement is observed. Lower bioavailability of oral corticosteroids should be taken into account when switching to the equivalent dose of oral corticosteroids.

Updated 05-Jul-2016

Hepatic Adverse Event Management Algorithm

Rule out non-inflammatory causes. If non-inflammatory cause, treat accordingly and continue I-O therapy. Consider imaging for obstruction.

Patients on IV steroids may be switched to an equivalent dose of oral corticosteroids (e.g. prednisone) at start of tapering or earlier, once sustained clinical improvement is observed. Lower bioavailability of oral corticosteroids should be taken into account when switching to the equivalent dose of oral corticosteroids.

[figure not shown]
*I-O therapy may be delayed rather than discontinued if AST/ALT ≤ 8 x ULN or T.bili ≤ 5 x ULN.

**The recommended starting dose for grade 4 hepatitis is 2 mg/kg/day methylprednisolone IV.

Updated 05-Jul-2016

Endocrinopathy Management Algorithm

Rule out non-inflammatory causes. If non-inflammatory cause, treat accordingly and continue I-O therapy. Consider visual field testing, endocrinology consultation, and imaging.

[figure not shown]

Patients on IV steroids may be switched to an equivalent dose of oral corticosteroids (e.g. prednisone) at start of tapering or earlier, once sustained clinical improvement is observed. Lower bioavailability of oral corticosteroids should be taken into account when switching to the equivalent dose of oral corticosteroids.

Updated 05-Jul-2016

Skin Adverse Event Management Algorithm

Rule out non-inflammatory causes. If non-inflammatory cause, treat accordingly and continue I-O therapy.

Patients on IV steroids may be switched to an equivalent dose of oral corticosteroids (e.g. prednisone) at start of tapering or earlier, once sustained clinical improvement is observed. Lower bioavailability of oral corticosteroids should be taken into account when switching to the equivalent dose of oral corticosteroids.

[figure not shown]
*Refer to NCI CTCAE v4 for term-specific grading criteria.

[^]If SJS/TEN is suspected, withhold I-O therapy and refer patient for specialized care for assessment and treatment. If SJS or TEN is diagnosed, permanently discontinue I-O therapy.

Updated 05-Jul-2016

Neurological Adverse Event Management Algorithm

Rule out non-inflammatory causes. If non-inflammatory cause, treat accordingly and continue I-O therapy.

Patients on IV steroids may be switched to an equivalent dose of oral corticosteroids (e.g. prednisone) at start of tapering or earlier, once sustained clinical improvement is observed. Lower bioavailability of oral corticosteroids should be taken into account when switching to the equivalent dose of oral corticosteroids.

Updated 05-Jul-2016

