4.5.2 Management Algorithms for Immuno-oncology Agents

I-O agents are associated with AEs that can differ in severity and duration from AEs caused by other therapeutic classes. Nivolumab, ipilimumab, and BMS-986205 are considered I-O agents in this protocol. Early recognition and management of AEs associated with I-O agents

may mitigate severe toxicity. Management algorithms have been developed from extensive experience with nivolumab and ipilimumab to assist investigators in assessing and managing the following groups of AEs:

- Gastrointestinal
- Renal
- Pulmonary
- Hepatic
- Endocrinopathies
- Skin
- Neurological

The clinical nature of AEs noted with BMS-986205 will determine the role of the above algorithms for use in toxicities related to its use in this study.

The algorithms recommended for utilization in this protocol are included in [Appendix 5](#).

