4.5.6 Guidelines for Permanent Discontinuation

Subjects will be required to permanently discontinue all study drugs for the following AEs:

- Clinical deterioration, as assessed by the investigator
- Any occurrence of serotonin syndrome
- Any Grade 3 non-skin, drug-related AE lasting > 7 days, or recurs with the following exceptions for laboratory abnormalities, neurologic toxicity, drug-related uveitis, pneumonitis, bronchospasm, hypersensitivity reactions, infusion reactions, endocrinopathies (and diarrhea and colitis for subjects receiving ipilimumab):
 - Grade 3 drug-related neurologic toxicity, uveitis, pneumonitis, bronchospasm, myocarditis, hypersensitivity reaction, or infusion reaction of any duration requires discontinuation; for subjects receiving ipilimumab, Grade 3 diarrhea and colitis of any duration also require discontinuation
 - Grade 3 drug-related endocrinopathies, adequately controlled with only physiologic hormone replacement do not require discontinuation. Adrenal insufficiency requires discontinuation regardless of control with hormone replacement.
 - Grade 3 drug-related laboratory abnormalities do not require treatment discontinuation except:
 - ◆ Grade 3 drug-related thrombocytopenia > 7 days or associated with bleeding requires discontinuation
 - ◆ Any drug-related liver function test (LFT) abnormality that meets the following criteria require discontinuation:
 - Grade ≥ 3 drug-related AST, ALT or Total Bilirubin requires discontinuation*
 - Concurrent AST or ALT $> 3 \times$ ULN and total bilirubin $> 2 \times$ ULN

* In most cases of Grade 3 AST or ALT elevation, study treatment will be permanently discontinued. If the investigator determines a possible favorable benefit/risk ratio that warrants continuation of study treatment, a discussion between the investigator and the BMS Medical Monitor/designee must occur.

- Any Grade 4 drug-related adverse event or laboratory abnormality (including but not limited to creatinine, AST, ALT, or Total Bilirubin), except for the following events which do not require discontinuation:
 - Grade 4 neutropenia ≤ 7 days
 - Grade 4 lymphopenia or leukopenia or asymptomatic amylase or lipase

- Isolated Grade 4 electrolyte imbalances/abnormalities that are not associated with clinical sequelae and are corrected with supplementation/appropriate management within 72 hours of their onset

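### Appendix 5 says to stop I-O therapy permanently on diagnosed SJS/TEN, but the required stopping list in Section 4.5.6 does not name it, so at Grade 3 the body text permits resumption

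*Combined protocol and SAP*

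**What the plan says.** **Appendix 5, skin algorithm footnote.** On suspicion: "If SJS/TEN is suspected, withhold I-O therapy and refer patient for specialized care for assessment and treatment". On diagnosis: "If SJS or TEN is diagnosed, permanently discontinue I-O therapy". The appendix describes its own standing: "These general guidelines constitute guidance to the Investigator".

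**Section 4.5.2.** This section brings the appendix into the protocol: "The algorithms recommended for utilization in this protocol are included in" Appendix 5. It also sets the scope: "Nivolumab, ipilimumab, and BMS-986205 are considered I-O agents in this protocol". It adds a qualifier, that the clinical nature of the adverse events seen with BMS-986205 will decide what role the algorithms play for that drug.

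**Section 4.5.6.** This is the list of events for which all study drugs must be stopped for good. Its Grade 3 rule begins "Any Grade 3 non-skin, drug-related AE lasting" more than 7 days. It also has a Grade 4 rule for any drug-related event, with a few exceptions, and a named stop that does not depend on grade: "Any occurrence of serotonin syndrome". SJS and TEN do not appear in it.

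**Sections 4.5.3 to 4.5.5.** Section 4.5.4 delays all study treatment for a Grade 3 drug-related skin event. It says that subjects outside the Section 4.5.6 criteria will be allowed to resume under Section 4.5.5. Table 4.5.3-1 lowers BMS-986205 by one level for other drug-related events of Grade 3 or above that do not meet Section 4.5.6, and keeps nivolumab and ipilimumab at the same dose. Section 4.5.3 rules out any reduction for subjects at 25 mg.

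**The concern.** Two parts of one protocol give different answers to the same clinical question. A site that works from Appendix 5 will not restart treatment after diagnosed SJS/TEN. A site that works from Section 4.5.6, the list the protocol calls required, will find that a Grade 3 case is not on it and that the resumption rules apply. The only explicit SJS/TEN stop therefore sits in the text with the weaker standing.

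What is at stake is re-exposure of a patient to the suspect drugs after a severe skin reaction. The event is not hypothetical here. Sections 1.4.4.4 and 1.5.2 report a treatment-related SJS death with BMS-986205 plus nivolumab, alongside deaths from myocarditis and hepatic failure. Section 4.5.6 has its own Grade 3 lines for myocarditis and for liver tests, the latter with a Medical Monitor route for AST/ALT. It has none for SJS.

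**Working it through.** No arithmetic applies. The check follows a diagnosed, drug-related case through the rules by grade and sets the result beside Appendix 5.

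| Grade | Body text (Sections 4.5.3 to 4.5.6) | Appendix 5 | Agree? |
|---|---|---|---|
| 4 | Permanent stop of all study drugs (Section 4.5.6, Grade 4 rule) | Permanent stop | Yes |
| 3 | Delay, then BMS-986205 down one level, then resumption permitted | Permanent stop | No |
| 2 or lower | Not assessed (see verdict) | Not assessed | No claim |

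**The Grade 3 row, step by step**

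1. *Is it a required stop?* The Section 4.5.6 Grade 3 rule covers non-skin events, and SJS/TEN is not named elsewhere in the list. The list does stop Grade 3 hypersensitivity reactions of any duration, but as an exception under the non-skin rule. The documents do not say whether SJS/TEN counts as one.
2. *Delay.* Section 4.5.4 delays all study drugs for a Grade 3 drug-related skin event.
3. *Dose.* Table 4.5.3-1 takes BMS-986205 down one level with antibody doses unchanged. At 25 mg there is no reduction (Section 4.5.3). Section 1.4.4.4 reports that 25 mg was opened for the Part 3 NSCLC cohort, so that case can arise.
4. *Resumption.* Section 4.5.5 permits it once the event has recovered to Grade 1 or baseline.
5. *Time limit.* A delay beyond 6 weeks is cause for permanent discontinuation (Sections 4.5.5 and 4.5.6). Section 4.5.6 allows extensions case by case, and allows longer delays for prolonged steroid tapers. The Medical Monitor must be consulted before a restart after 6 weeks. A case that recovers within 6 weeks does not reach this limit.
6. *Discretion.* Section 3.5 requires a stop if the investigator judges that an adverse event makes continuing contrary to the subject's interest. Section 4.5.3 allows more conservative modification. Section 4.5.5 calls for case-by-case review with the Medical Monitor when an event carries clinical risk. Section 4.5.6 itself lists "Clinical deterioration, as assessed by the investigator". Each depends on a judgement, and none makes this diagnosis in itself a reason to stop.

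**Result.** At Grade 3 the body text permits a restart that Appendix 5 rules out. The time limit and the discretionary provisions narrow the opening but do not close it.

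**Precedent in the same list.** Serotonin syndrome is a named stop at any grade, although Section 3.4.2 says that no case has been seen with BMS-986205. A named stop for one diagnosis therefore already fits the structure of Section 4.5.6.

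**The case against.** The strongest reply is that the stop is already in the protocol. Appendix 5 is part of it, Section 4.5.2 recommends it, and Section 9.1.1 requires the study to be run as the protocol describes. The body rules are general: Section 4.5.5 says that subjects may resume, and the dose table is described as general guidance that can be applied more strictly. A specific instruction for one diagnosis can be read as prevailing over a general permission. Serotonin syndrome also belongs to none of the seven algorithm groups in Section 4.5.2, so its place in the body text has its own explanation.

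Much of this stands. Nothing in the protocol tells anyone to restart after SJS/TEN, and a careful investigator would very probably not do so. The Section 4.5.2 qualifier also makes the reach of Appendix 5 to BMS-986205 less than categorical. The reply does not settle which text governs. Appendix 5 calls itself guidance, Section 4.5.4 points to Section 4.5.6 for required stops, and it then says that subjects who do not meet those criteria will be allowed to resume. The specific rule is the non-binding one.

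A reader might infer two stronger things:

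- *That the body text leaves SJS/TEN of Grade 2 or lower with no required hold.* The Section 4.5.4 Grade 2 delay is indeed limited to non-skin events, and the table row for other events starts at Grade 3. But the documents do not give the CTCAE grading of SJS/TEN, and the skin flowchart to which the footnote belongs is not visible. Whether any such patients could exist cannot be determined.
- *That the reported death came about through this gap.* The documents give neither the grade course of that case nor any mention of a restart.

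**Conclusion.** The point holds at Grade 3. For drug-related SJS/TEN, the required list and the rules that depend on it permit resumption, while the appendix guidance calls for a permanent stop on diagnosis. Grade 4 is consistent across both. No claim is made for Grade 2 or lower.

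The conclusion rests on two assumptions. The first is that SJS/TEN is handled as a skin event and not as a hypersensitivity reaction, which would already be a stop at Grade 3. The second is that the Appendix 5 footnote applies at Grade 3. Its visible wording is triggered by diagnosis and carries no grade limit, but the flowchart could not be checked.

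The practical size is small and cannot be put as a rate. SJS is 1 of the 3 treatment-related deaths in Section 1.5.2. It occurred after the 15-Nov-2017 cut-off, so the 397 subjects treated with the combination by that date are not a valid denominator. The documents give no count of SJS/TEN below Grade 4. No endpoint, sample size or analysis is affected. This is a minor to should-fix safety harmonisation.

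**What to change.** Two lines at the next amendment would bring the body text into step with Appendix 5:

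- **Section 4.5.6:** add *any diagnosed drug-related SJS or TEN, regardless of grade*, next to the serotonin syndrome line. The drug-related limit matters, because without it a case clearly caused by a concomitant medicine would force a stop. Section 4.5.5 and the relevant row of Table 4.5.3-1 both defer to Section 4.5.6, so they follow without further edits.
- **Section 4.5.4:** add *suspected SJS/TEN (withhold and refer for specialized care)* to the list of delays for all study drugs. This carries over the Appendix 5 step on suspicion and does not depend on how the event is graded.

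The cost is one line in each section, with no extra data, visits or patients.

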APPENDIX 6 REVISED INTERNATIONAL PROGNOSTIC INDEX (IPI) SCALE*

Composite score was determined by assigning 1 point for each of the following factors:

- Age > 60 years
- ECOG PS > 2
- Elevated Serum LDH
- More than 1 extranodal site
- Stage III/IV disease (Ann Arbor staging)

APPENDIX 7 CYP3A4, CYP1A2 AND CYP2B6 GUIDANCE

The lists below are not meant to be all inclusive. Please consult individual drug labels for further information. Additional information is also available at:

<http://www.fda.gov/Drugs/DevelopmentApprovalProcess/DevelopmentResources/DrugInteractionsLabeling/ucm093664.htm>

Table 1: Classification of In Vivo Inhibitors of CYP Enzymes

CYP Enzymes	Strong Inhibitors ^a ≥ 5-fold Increase in AUC or > 80% Decrease in CL	Moderate Inhibitors ^b ≥ 2 but < 5-fold Increase in AUC or 50-80% Decrease in CL	Weak Inhibitors ^c ≥ 1.25 but < 2-fold Increase in AUC or 20-50% Decrease in CL
CYP3A	Boceprevir, clarithromycin, conivaptan, grapefruit juice, ^d indinavir, itraconazole, ketoconazole, lopinavir/ritonavir, mibefradil, ^e nefazodone, nelfinavir, posaconazole, ritonavir, saquinavir, telaprevir, telithromycin, voriconazole	Amprenavir, aprepitant, atazanavir, ciprofloxacin, darunavir/ritonavir, diltiazem, erythromycin, fluconazole, fosamprenavir, grapefruit juice, ^d imatinib, verapamil	Alprazolam, amiodarone, amlodipine, atorvastatin, bicalutamide, cilostazol, cimetidine, cyclosporine, fluoxetine, fluvoxamine, ginkgo, ^f goldenseal, ^f isoniazid, nilotinib, oral contraceptives, ranitidine, ranolazine, tipranavir/ritonavir, zileuton
CYP1A2	ciprofloxacin, enoxacin, fluvoxamine ^g , zafirlukast	methoxsalen, mexiletine, oral contraceptives	acyclovir, allopurinol, cimetidine, peginterferon alpha-2a, piperine, zileuton

Please note that this is not an exhaustive list.

a A strong inhibitor for a specific CYP is defined as an inhibitor that increases the AUC of a substrate for that CYP by equal or more than 5-fold.

b A moderate inhibitor for a specific CYP is defined as an inhibitor that increases the AUC of a sensitive substrate for that CYP by less than 5-fold but equal to or more than 2-fold.

^c A weak inhibitor for a specific CYP is defined as an inhibitor that increases the AUC of a sensitive substrate for that CYP by less than 2-fold but equal to or more than 1.25-fold.

^d The effect of grapefruit juice varies widely among brands and is concentration, dose, and preparation dependent. Studies have shown that it can be classified as a “strong CYP3A inhibitor” when a certain preparation was used (eg, high dose, double strength) or as a “moderate CYP3A inhibitor” when another preparation was used (eg, low dose, single strength).

^e Withdrawn from the United States market because of safety reasons

^f Herbal product

^g Strong inhibitor of CYP1A2 and CYP2C19, and moderate inhibitor of CYP2D6 and CYP3A4.

Abbreviations: AUC = area under the concentration-time curve; CYP = cytochrome P450.

Table 2: Classification of In Vivo Inducers of CYP Enzymes

CYP Enzymes	Strong Inducers ≥ 80% Decrease in AUC	Moderate Inducers 50-80% Decrease in AUC	Weak Inducers 20-50% Decrease in AUC
CYP3A	Avasimibe, ^a carbamazepine, phenytoin, rifampin, St. John's wort ^b	Bosentan, efavirenz, etravirine, modafinil, naftillin	Amprenavir, aprepitant, armodafinil, echinacea, ^c pioglitazone, prednisone, rufinamide
CYP1A2		Phenytoin ^d , rifampin ^e , ritonavir ^f , smoking, teriflunomide	

Please note that this is not an exhaustive list.

^a Not a marketed drug.

^b The effect of St. John's wort varies widely and is preparation dependent.

^c Herbal product.

^d Strong inducer of CYP3A and moderate inducer of CYP1A2, CYP2C19.

^e Strong inducer of CYP2C19, CYP3A, and moderate inducer of CYP1A2, CYP2B6, CYP2C8, CYP2C9.

^f Strong inducer of CYP2C19 and moderate inducer of CYP1A2, CYP2B6, CYP2C9.

Abbreviations: AUC = area under the concentration-time curve; CYP = cytochrome P450.

Table 3: Examples of Sensitive In Vivo CYP Substrates and CYP Substrates with Narrow Therapeutic Range

CYP Enzymes	Sensitive Substrates ^a	Substrates with Narrow Therapeutic Range ^b
CYP3A	Alfentanil, aprepitant, budesonide, buspirone, conivaptan, darifenacin, darunavir, dasatinib, dronedarone, eletriptan, eplerenone, everolimus, felodipine, indinavir, fluticasone, lopinavir, lovastatin, lurasidone, maraviroc, midazolam, nisoldipine, quetiapine, saquinavir, sildenafil, simvastatin, sirolimus, tolvaptan, tipranavir, triazolam, vardenafil	Alfentanil, astemizole, ^c cisapride, ^c cyclosporine, dihydroergotamine, ergotamine, fentanyl, pimozide, quinidine, sirolimus, tacrolimus, terfenadine ^c
CYP2B6	Bupropion, efavirenz	

Please note that this is not an exhaustive list.

^a Sensitive CYP substrates refers to drugs whose plasma AUC values have been shown to increase 5-fold or higher when co-administered with a known CYP inhibitor.

^b CYP substrates with narrow therapeutic range refers to drugs whose exposure-response relationship indicates that small increases in their exposure levels by the concomitant use of CYP inhibitors may lead to serious safety concerns (eg, Torsades de Pointes).

^c Withdrawn from the United States market because of safety reasons.

Abbreviations: AUC = area under the concentration-time curve; CYP = cytochrome P450.

APPENDIX 8 MEDICATIONS ASSOCIATED WITH QT PROLOGATION

The list below is not meant to be all inclusive. Please consult individual drug labels for further information.

quinidine, procainamide, disopyramide,
amiodarone, sotalol, ibutilide, dofetilide,
erythromycins, clarithromycin,
chlorpromazine, haloperidol, mesoridazine, thioridazine, pimozide,
cisapride, bepridil, droperidol, methadone, arsenic, chloroquine, domperidone,
halofantrine, levomethadyl, pentamidine, sparfloxacin, lidoflazine

APPENDIX 9 P-GP AND BCRP GUIDANCE

The list below is not meant to be all inclusive. Please consult individual drug labels for further information. Additional information is also available at:

<http://www.fda.gov/Drugs/DevelopmentApprovalProcess/DevelopmentResources/DrugInteractionsLabeling/ucm080499.htm>

Table 1: Examples of In Vivo Substrates for Selected Transporters

Transporter	Gene	Substrate
P-gp	ABCB1	Aliskiren, ambrisentan, colchicine, dabigatran etexilate, digoxin, everolimus, fexofenadine, imatinib, lapatinib, maraviroc, nilotinib, posaconazole, ranolazine, saxagliptin, sirolimus, sitagliptin, talinolol, tolvaptan, topotecan
BCRP	ABCG2	Methotrexate, mitoxantrone, imatinib, irinotecan, lapatinib, rosuvastatin, sulfasalazine, topotecan

Please note that this is not an exhaustive list.

Abbreviations: BCRP = breast cancer resistance protein; P-gp = P-glycoprotein.

